9.1.2. Main Analyses

The main analysis for the primary estimand will be conducted based on the Full Analysis Set 1, using treatment policy to address all ICEs. All CAPS-5 total score data collected through Week 12 regardless of ICEs will be used in the analysis, including the CAPS-5 total score data collected after an ICE. Using the main ICE of treatment discontinuation as the example, [Table 5](#) describes the detailed data mapping method for CAPS-5 total score scores following treatment discontinuation.

Table 5. Data mapping for CAPS-5 total score following treatment discontinuation for the main analyses.

Intercurrent event	CAPS-5 total score data mapping
If participant discontinues both study intervention and the study	CAPS-5 total score at E/D or any unscheduled visit will be mapped to Week 4 or Week 12, according to the windowing rule in Section 7.2.3 .
If participant discontinues study intervention prior to Week 4 but remains in the study	CAPS-5 total score at E/D visit, any unscheduled visit, the additional efficacy follow-up for Week 4, or efficacy follow-up visit for Week 12 will be mapped to Week 4 or Week 12, according to the windowing rule in Section 7.2.3 .
If participant discontinues study intervention between Week 4 and Week 12 but remains in the study	CAPS-5 total score at E/D visit, any unscheduled visit, or efficacy follow-up visit for Week 12 will be mapped to Week 12, according to the windowing rule in Section 7.2.3 .

A mixed-effect model with repeated measures (MMRM) will be used to analyze the primary efficacy endpoint, change in CAPS-5 total score from Baseline to Week 12.

$$dCAPS5TotalScore_{ij} = \alpha_i + \beta_1 * baseCAPS5TotalScore_i + \beta_2 * week_j + \beta_3 * treatment_i + \beta_4 * treatment_i * week_j + \beta_5 * baseCAPS5TotalScore_i * week_j + \beta_6 * stratum_i + \beta_7 * stratum_i * week_j + \varepsilon_{ij}$$

The model will include the CAPS-5 total score change from Baseline to Week 12 ($dCAPS5TotalScore_{ij}$) as the dependent variable; randomized treatment group ($treatment_i$), CAPS-5 total score at Baseline ($baseCAPS5TotalScore_i$), week (as a discrete factor, $week_j$), treatment group by week interaction ($treatment_i * week_j$), baseline by week interaction ($baseCAPS5TotalScore_i * week_j$), randomization stratum ($stratum_i$), and stratum by week interaction ($stratum_i * week_j$) as fixed effects, and week as a repeated effect.

SAS Proc Mixed with restricted maximum likelihood estimation (REML) will be used and an unstructured within-participant covariance structure will be applied to model the correlation

Jazz Pharmaceuticals
 {Statistical Analysis Plan - Protocol #}JZP150-201-02

among repeated measurements. If the model fails to converge on the default Newton-Raphson algorithm, the alternative Fisher scoring algorithm should be explored before considering other variance-covariance structures ([Lu and Mehrotra 2010](#)). The Kenward-Roger approximation will be used to estimate denominator degrees of freedom for tests of fixed effects. Missing data will not be explicitly imputed and will be handled with the MMRM modeling.

LS means, SE and 95% CI for Week 12 will be provided for each randomized treatment group. The difference between the LS means of an active treatment group and placebo for Week 12, along with the SE of the difference, 95% CI and associated p-value corresponding to testing the hypothesis of no difference between the treatment groups will also be provided. Summary statistics of CAPS-5 total score by time point for each treatment group based on the Full Analysis Set 1 will also be provided.

If the unstructured covariance fails to converge, the following covariance structures will be tested in order:

- Toeplitz with heterogeneity by visit
- Autoregressive with heterogeneity by visit
- Compound symmetry with heterogeneous variances by visit
- Toeplitz
- Autoregressive
- Compound symmetry without heterogeneous variances by visit

If structured covariance matrix is used, a sandwich variance estimator will be applied simultaneously to address the potential mis-specification of the covariance matrix.

A box plot of the change in the CAPS-5 total score from Baseline to end to Week 12 by randomized treatment group will be presented. The CAPS-5 total score data will also be summarized by time point and the change from baseline to each time point will be displayed as a figure.

Following provides the example SAS code for the MMRM model used in the main analysis.

```
PROC MIXED DATA =ANAL;
  CLASS PATIENT TRT WEEK STRATUM;
  MODEL CHG = BASE TRT WEEK TRT*WEEK BASE* WEEK STRATUM STRATUM*
    WEEK / DDFM=KR RESIDUAL OUTP=RESIDUAL;
  REPEATED WEEK/TYPE=UN SUB=PATIENT;
  LSMEANS TRT*WEEK / CL DIFF ALPHA=0.05;
  RUN;
```

The option of “EMPIRICAL” will be applied in the PROC MIXED procedure above if structured covariance matrix is used.

9.1.3. Sensitivity Analyses

9.1.3.1. Tipping Point Analysis

The main efficacy analysis of the primary and key secondary efficacy estimand includes all CAPS-5 total score, CGI-S score, and PGI-S score data collected following any ICEs for participants who remain in the study and assumes that any remaining missing data due to ICEs is missing at random (MAR). To examine the departure of the main efficacy analysis results from

Jazz Pharmaceuticals
 {Statistical Analysis Plan - Protocol #}JZP150-201-02

the MAR assumption in the MMRM modeling, a tipping point analysis will be performed to ‘stress test’ the robustness of the main efficacy analysis based on the Full Analysis Set 1.

This method involves a 3-step approach:

Step 1: The MCMC method will be used in conjunction with the IMPUTE=MONOTONE option to create an imputed dataset with a monotone missing pattern.

Step 2: Using the monotone dataset from step 1, missing data will be imputed using the MONOTONE REGRESSION method. Participants who experienced an ICE such as treatment discontinuation earlier than Week 12 will have missing data imputed first assuming a MAR mechanism.

Step 3: A “marginal delta” or “shift” will be added to Week 12 for one specific JZP150 treatment arm prior to analyzing the imputed datasets (number of imputations=20) and combining the results using the same MAR assumption and MMRM modeling as in step 2. The deltas to be investigated are multiples of the observed treatment effect. If the absolute value of LS Mean Difference at week 12 from the MMRM modeling in the main analysis is X, the deltas to be investigated will range from -X to +3X for one specific JZP150 treatment arm, in increments of 0.2X, for example. The increment or range may be further refined based on the analysis results and the location of tipping point. The X from the JZP150 4 mg vs placebo comparison in the main analysis will also be used for the tipping point analysis between JZP150 0.3 mg vs placebo. The imputed datasets will be analyzed using the same MMRM model described in [Section 9.1.2](#). Results will be combined using Rubin’s rule ([Rubin 1987](#)) for the estimation of treatment effect at Week 12.

Step 1 may be omitted if missing data are completely monotone.

The imputation model for step 1 and step 2 will include the auxiliary variable randomization stratum and the values of the analyzed parameter at baseline and planned visits up to Week 12. The imputation in both steps will be performed separately for each treatment arm. The number of imputations will be 20 in step 1 and 1 in step 2. If step 1 is omitted, then the number of imputations in step 2 will be 20.

JZP150 and placebo arms will be imputed 20 times based on the MAR assumption. For each of the imputations, the relevant deltas will be added to Week 12 for the JZP150 treatment arm. The modified imputations will be then analyzed using the same MMRM model in step 2 and the results will be combined.

The values of the imputed variables will be restricted within the ranges of minimum and maximum possible values.

The following SAS code can be used to perform the tipping point analysis.

```
%MACRO TPA1 (DATA=, SMIN=, SMAX=, SINC=, OUT=);
DATA &OUT;
SET _NULL_;
RUN;
/*----- # OF SHIFT VALUES -----*/
%LET NCASE= %SYSEVALF( (&SMAX-&SMIN)/&SINC, CEIL );
/*----- IMPUTED DATA FOR EACH SHIFT -----*/
```

Jazz Pharmaceuticals
 {Statistical Analysis Plan - Protocol #}JZP150-201-02

```
%DO JC=0 %TO &NCASE; /*NCASE IS THE NUMBER OF TOTAL SHIFTS TO BE
EVALUATED*/
%LET SJ= %SYSEVALF( &SMIN + &JC * &SINC); /*SJ IS THE SHIFT VALUE*/
PROC MI DATA=&DATA SEED=439384924 NIMPUTE=20 OUT=MONO
MINIMUM=0 0 0
MAXIMUM=1 80 80 80
MINMAXITER=9000;
MCMC IMPUTE=MONOTONE NBITER=200 NITER=200;
VAR STRATUM BASE WEEK4 WEEK12;
BY TRT;
RUN;
PROC MI DATA=MONO SEED=439384924 NIMPUTE=1 OUT=OUTMI
MINIMUM=0 0 0
MAXIMUM=1 80 80 80
MINMAXITER=9000;
CLASS TRT;
VAR STRATUM TRT BASE WEEK4 WEEK12;
MONOTONE REGRESSION (BASE STRATUM WEEK4 WEEK12);
MNAR ADJUST(WEEK12 / SHIFT=&SJ. ADJUSTOBS=(TRT='1' '2'));
BY TRT _IMPUTATION_;
RUN;
DATA OUTMI;
SET OUTMI;
SHIFT= &SJ;
RUN;
DATA &OUT;
SET &OUT OUTMI;
RUN;
%END;
%MEND TPA1;

%TPA1 (DATA=ANAL_MONO, SMIN=-&X., SMAX=3&X., SINC=0.2&X., OUT= TPA1);

/*CALCULATE CHG AND TRANSPOSE DATA BEFORE RUNNING MMRM MODEL*/
PROC MIXED DATA= ANAL_TPA1;
CLASS PATIENT TRT WEEK STRATUM;
MODEL CHG = BASE TRT WEEK TRT*WEEK BASE* WEEK STRATUM STRATUM*
WEEK / DDFM=KR RESIDUAL OUTP=RESIDUAL;
REPEATED WEEK/TYPE=UN SUB=PATIENT;
LSMEANS TRT*WEEK / CL DIFF ALPHA=0.05;
ODS OUTPUT DIFFS=LSDIFFS (where=(TRT=0 and TRT=1 and WEEK=12 and
_WEEK=12));
BY SHIFT _IMPUTATION_;
RUN;

PROC MIANALYZE DATA=LSDIFFS;
```

Jazz Pharmaceuticals
 {Statistical Analysis Plan - Protocol #}JZP150-201-02

```
MODELEFFECTS ESTIMATE;
STDERR STDERR;
BY SHIFT;
ODS OUTPUT PARAMETERESTIMATES=TIPDIFFS;
RUN;
```

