9.1.3.2. Control-based Pattern Mixture Imputation

For both the primary and key secondary efficacy endpoints, a control-based pattern mixture model will be used to explore the possibility of the missing data being missing not at random (MNAR) for the participants who discontinued study intervention but provided no post-discontinuation efficacy data for the main analysis.

These participants will be categorized based on their reason of treatment discontinuation. If the reason is ‘lack of efficacy’ or ‘adverse events’, the participant will be categorized as ‘treatment-related discontinuation’. If it is due to any other reason, the participant will be categorized as ‘treatment-unrelated discontinuation’.

For the participants having treatment-related discontinuation, missing data will be imputed using the ‘copy reference’ imputation where the mean and variance based on the placebo group (reference) will be assumed for both Week 4 and Week 12 data for the primary endpoint, for example ([O’Kelly and Ratitch, 2014](#)). For the participants having treatment-unrelated discontinuation, missing data will be imputed assuming MAR.

Similar to step 1 and step 2 in tipping point analysis, 20 imputed datasets will be generated assuming a MAR mechanism for missing data. For the participants having treatment-related discontinuation, the imputed Week 4 and Week 12 data will be discarded in each of these 20 datasets and replaced by MNAR imputations. The final imputed datasets with a mixture of MAR and MNAR imputations will be analyzed separately using the MMRM model specified in [Section 9.1.2](#).

The MIANALYZE procedure will be used to generate valid statistical inferences by combining results from the 20 analyses.

The following SAS code can be used for the MNAR imputation.

```
PROC MI DATA=ANAL_COMPL SEED=439384924 NIMPUTE=1 OUT=ANAL_MNAR;
MINIMUM = 1 0 0 0 ;
MAXIMUM = 2 80 80 80. ;
CLASS TRT;
VAR STRATUM BASE WEEK4 WEEK12;
MONOTONE REGRESSION (/DETAILS);
MNAR MODEL(WEEK4 WEEK12 / MODELOBS= (TRT='0'));
BY _IMPUTATION_;
RUN;
```

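### With 20 imputations the reported tipping point commonly moves by a grid step with the random seed, and the example code does not implement the prose

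*SAP*

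**What the plan says.** SAP 9.1.3.1 imputes missing scores under MAR and adds a delta at Week 12 "prior to analyzing the imputed datasets (number of imputations=20) and combining the results", refitting the main MMRM. The number of imputations is set in the prose: "The number of imputations will be 20 in step 1 and 1 in step 2". If step 1 is omitted, step 2 uses 20. The code fixes the same number and one seed: "PROC MI DATA=&DATA SEED=439384924 NIMPUTE=20 OUT=MONO".

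The delta "will be added to Week 12 for one specific JZP150 treatment arm". It runs from -X to +3X, in steps of 0.2X as an example, where X is the absolute Week 12 difference for 4 mg versus placebo in the main analysis. Both doses are to be examined. Step and range may be refined after seeing results, and imputed values are to stay within the scale's limits.

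The code, introduced as code that can be used, contains:
- the shift, "MNAR ADJUST(WEEK12 / SHIFT=&SJ. ADJUSTOBS=(TRT='1' '2" (both codes 1 and 2);
- the grid, "SMIN=-&X., SMAX=3&X., SINC=0.2&X";
- the result filter, "where=(TRT=0 and TRT=1 and WEEK=12 and" `_WEEK=12`.

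SAP 9.1.3.2 shows that placebo is coded 0, through its reference-arm statement "MNAR MODEL(WEEK4 WEEK12 / MODELOBS= (TRT='0".

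**The concern.** SAP 7.7 drops the protocol's time-dependent multiple imputation and reduces its two-dimensional tipping point to one dimension. The MNAR checks left for the primary and key secondary results are this analysis and the control-based imputation. SAP 7.7 also says that little efficacy follow-up was collected after intercurrent events, so missing data may matter.

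A tipping point is the first delta at which p reaches 0.05. It inherits the simulation error of both the pooled estimate and its standard error, and because only the imputed values are shifted, that error is magnified on the delta scale. The SAP gives no reason for 20 and no Monte Carlo criterion. The permitted finer grid would not help, since it would resolve steps smaller than the noise. Separately, a programmer following the printed code would not obtain the planned output.

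**Working it through.** **Plan's own figures.** Difference 6, SD 10.5, two-sided 0.05, completers 75/38/75 (SAP 5.3). Noncentrality is 6/(10.5·√(1/75+1/75)) = 3.50 for 4 mg and 6/(10.5·√(1/75+1/38)) = 2.87 for 0.3 mg. The t-test power is 93.5% and 81.2%, against 93.4% and 80.9% stated. 188/0.70 = 268.6, consistent with 270. The planning inputs reproduce.

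**Simulation inputs.** From the SAP: 108/54/108 randomized and SD 10.5. X is set to 6, the planned difference, or to 4.5. Assumed, not in the documents: Week 12 missing in 30% of each arm (half of these also missing Week 4), Week 4–12 correlation of change 0.4–0.8, baseline SD 8, baseline–change correlation -0.3, 35% in one stratum, no truncation at 0–80. Each arm is imputed by Bayesian monotone regression. The Week 12 contrast comes from the covariate-adjusted model and is pooled by Rubin's rules, T = U + (1+1/m)B. There are 500 seeds per setting.

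**Arithmetic for 4 mg, X=6, correlation 0.6.** The pooled SE is 1.592 and B/T is 0.236, so B = 0.236 × 1.592² = 0.598. The Monte Carlo SD of the estimate is √(B/m): √(0.598/20) = 0.173 (simulated 0.168), falling to 0.077 at m=100 and 0.055 at m=200. A shift of 1 point moves the contrast by only 0.299, so the tipping delta is about (6 − 1.96×1.592)/0.299 = 9.6. Letting the SE grow with the shift gives 9.48. On the delta scale the error is at least 0.173/0.299 = 0.58. Noise in B raises this to the simulated 0.71.

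| Dose, X | Correlation | Large-m tipping delta | Seed SD, m=20 | m=100 | m=200 | Grid values, m=20 | Grid values, m=200 |
|---|---|---|---|---|---|---|---|
| 4 mg, 6 | 0.4 | 9.42 | 0.80 | 0.34 | 0.23 | 1.2X–2.2X | 1.6X–1.8X |
| 4 mg, 6 | 0.6 | 9.48 | 0.71 | 0.32 | 0.21 | 1.4X–2.0X | 1.6X–1.8X |
| 4 mg, 6 | 0.8 | 9.60 | 0.61 | 0.28 | 0.19 | 1.4X–2.0X | 1.6X–1.8X |
| 4 mg, 4.5 | 0.6 | 4.63 | 0.73 | 0.32 | 0.22 | 0.6X–1.6X | 1.0X–1.2X |
| 0.3 mg, 6 | 0.6 | 6.66 | 1.16 | 0.51 | 0.33 | 0.6X–1.6X | 1.0X–1.4X |

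The step is 1.2 points at X=6 and 0.9 at X=4.5. In the second row, m=20 gave 1.4X, 1.6X, 1.8X and 2.0X in 46, 268, 176 and 10 of 500 seeds. Two seeds would therefore disagree with probability 1 − (46²+268²+176²+10²)/500² = 0.58. For 0.3 mg (5, 41, 113, 203, 117, 21) the figure is 0.72. With m=200 these fall to 0.33 and 0.15.

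**Code against prose.**
- *Filter.* One variable cannot equal 0 and 1 at once, so no rows reach PROC MIANALYZE. Only code 1 is named, so the other dose is never extracted.
- *Grid.* `3&X.` and `0.2&X.` concatenate. At X=6 they give 36 and 0.26. The number of steps is ⌈(36+6)/0.26⌉ = 162, so there are 163 shifts, ending at -6 + 162×0.26 = 36.12. The prose intends (18+6)/1.2 = 20 steps, or 21 shifts ending at 18. Any X with a decimal point fails: X=5.3 gives `0.25.3`, which is not a number.
- *Limits.* The first PROC MI has four variables, three minima and four maxima. The second has five variables, three minima and four maxima. The code in SAP 9.1.3.2 has four of each.
- *Arms.* The prose shifts one dose and the code shifts both. The 4 mg tipping delta is 9.48 either way.

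**The case against.** The strongest defence is that 20 is a prespecified choice with a prespecified seed, so the result is repeatable and cannot be chosen after the fact. The analysis lies outside the testing sequence, no cut-off for robustness is set, and SAP 7.7 promises estimates, SEs and intervals at every delta, so readers see the whole curve. All of this stands. It limits the consequence but does not make the reported value precise.

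The 30% is also open to challenge. In the documents it is dropout from dosing, not missing Week 12 scores. Treatment policy keeps off-treatment data, and CAPS-5 scores on Days 57–112 map to Week 12. With 15% missing and X=6, the 4 mg tipping delta is about 20.1 (seed SD 0.74), beyond 3X = 18. In 497 of 500 seeds at m=20 no tipping point was found on the grid. The seed then hardly matters to the conclusion.

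Three stronger readings are tempting and unsupported:
- *That Monte Carlo error exceeds the grid step.* Every seed SD above is below its step. At X=6 and correlation 0.6, 268+176 = 444 of 500 seeds fell on two adjacent values.
- *That shifting both doses biases the result.* It leaves the pairwise contrast essentially unchanged.
- *That the code could silently distort a conclusion.* An empty dataset or an invalid increment stops the run. A whole-number X would run, but with a visibly wrong grid. The code is offered only as usable, and the prose is right on arm, grid and doses.

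A character lost in reading the PDF, such as an underscore before the second `TRT` or an entry in a limits list, cannot be excluded. Underscores and asterisks survive elsewhere in the same block, so the source file should be checked. The control-based analysis also uses 20 imputations, but its Monte Carlo error was not computed and nothing is claimed about it.

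**Conclusion.** The point holds as one of precision and specification, and it does not touch the primary analysis. With 30% missing Week 12 data, 20 imputations leave a seed SD of about 0.6–0.8 points for 4 mg (correlations 0.4–0.8) and about 1.2 points for 0.3 mg (correlation 0.6), against a step of 1.2 at X=6. One-step changes with the seed are common. In a borderline case, such as 4 mg at X=4.5, the reported value ranged over six grid values.

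More imputations cannot stop a true tipping point near a grid boundary from falling either side of it. At m=200 the 4 mg results were confined to two adjacent values, and for 0.3 mg 461 of 500 seeds agreed. These sizes depend on the assumed missingness, correlation and effect. The mismatches between code and prose depend on none of them, only on the code being as printed.

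**What to change.** - Set NIMPUTE to at least 100 in step 1 (200 preferred for 0.3 mg), or in step 2 if step 1 is omitted. Change the prose to match and report the Monte Carlo error of the estimate and the tipping delta.
- Pass `%SYSEVALF(3*&X)` and `%SYSEVALF(0.2*&X)`.
- Filter on `TRT=0 and _TRT=<dose> and WEEK=12 and _WEEK=12`, once per dose, and reverse the sign. Plain DIFF lists each pair once with the lower level first, so a filter with the dose in `TRT` and placebo in `_TRT` would again return nothing. Recoding placebo as the last level is the alternative.
- Give one MINIMUM and one MAXIMUM per VAR variable in both PROC MI calls.
- Set ADJUSTOBS to the single dose being tested and run the macro once per dose.

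The cost is minutes of computing time and a corrected code block. No data collection or primary analysis changes.

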9.1.3.2. Control-based Pattern Mixture Imputation

For both the primary and key secondary efficacy endpoints, a control-based pattern mixture model will be used to explore the possibility of the missing data being missing not at random (MNAR) for the participants who discontinued study intervention but provided no post-discontinuation efficacy data for the main analysis.

These participants will be categorized based on their reason of treatment discontinuation. If the reason is ‘lack of efficacy’ or ‘adverse events’, the participant will be categorized as ‘treatment-related discontinuation’. If it is due to any other reason, the participant will be categorized as ‘treatment-unrelated discontinuation’.

For the participants having treatment-related discontinuation, missing data will be imputed using the ‘copy reference’ imputation where the mean and variance based on the placebo group (reference) will be assumed for both Week 4 and Week 12 data for the primary endpoint, for example ([O’Kelly and Ratitch, 2014](#)). For the participants having treatment-unrelated discontinuation, missing data will be imputed assuming MAR.

Similar to step 1 and step 2 in tipping point analysis, 20 imputed datasets will be generated assuming a MAR mechanism for missing data. For the participants having treatment-related discontinuation, the imputed Week 4 and Week 12 data will be discarded in each of these 20 datasets and replaced by MNAR imputations. The final imputed datasets with a mixture of MAR and MNAR imputations will be analyzed separately using the MMRM model specified in [Section 9.1.2](#).

The MIANALYZE procedure will be used to generate valid statistical inferences by combining results from the 20 analyses.

The following SAS code can be used for the MNAR imputation.

```
PROC MI DATA=ANAL_COMPL SEED=439384924 NIMPUTE=1 OUT=ANAL_MNAR;
MINIMUM = 1 0 0 0 ;
MAXIMUM = 2 80 80 80. ;
CLASS TRT;
VAR STRATUM BASE WEEK4 WEEK12;
MONOTONE REGRESSION (/DETAILS);
MNAR MODEL(WEEK4 WEEK12 / MODELOBS= (TRT='0'));
BY _IMPUTATION_;
RUN;
```

9.1.3.3. Non-parametric Analysis

Non-parametric analysis may be performed to examine the departure from the parametric assumption for the MMRM model used in the main analysis of the primary efficacy estimand, if

Jazz Pharmaceuticals
 {Statistical Analysis Plan - Protocol #}JZP150-201-02

there is strong evidence of non-normality. In this sensitivity analysis, the p-value for comparing treatments for the primary endpoint will be reported from a non-parametric MMRM model with the response and baseline covariate variables replaced by their ranks. In the event of ties in the baseline or change from baseline, average ranks will be used. The ranks will be used in the MMRM with the rank for the change from baseline as the dependent variable; treatment, week (as a discrete factor), treatment group by week interaction, randomization stratum and ranked baseline CAPS-5 total score as fixed effects. P-values will be presented from the rank-based MMRM. The estimated median difference between the change in CAPS-5 total score between each treatment group and placebo, and asymptotic 95% CIs will be presented using the Hodges-Lehmann estimator ([Hodges and Lehmann 1962](#)).

The following SAS code will be used.

```
PROC RANK DATA =ANAL OUT=RANKED TIES=MEAN;
  VAR BASE CHG;
  RANKS RBASE RCHG;
  RUN;
```

```
PROC MIXED DATA=RANKED;
  CLASS PATIENT TRT WEEK STRATUM;
  MODEL RCHG = RBASE TRT WEEK TRT*WEEK RBASE* WEEK STRATUM
  STRATUM* WEEK / DDFM=KR RESIDUAL OUTP=RESIDUAL;
  REPEATED WEEK/TYPE=UN SUB=PATIENT;
  RUN;
```

An estimate of the median difference between treatments for the primary endpoint will be reported using Hodges-Lehmann analysis.

```
PROC NPAR1WAY HL ALPHA=.05 DATA=ANAL;
  CLASS TRT;
  VAR CHG;
  RUN;
```

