4.2.1. Primary Estimand

The primary estimand of the study is defined as:

- Treatment: 0.3 mg and 4 mg of JZP150, and placebo.
- Population: Participants with PTSD (as defined in the eligibility criteria).
- Variable (endpoint): CAPS-5 total score change from Baseline to Week 12.
- ICEs: The main ICE treatment discontinuation will be addressed by treatment policy (primary strategy) and hypothetical approach (alternative strategy). Other possible ICEs are defined in [Section 7.6](#).

Jazz Pharmaceuticals
{Statistical Analysis Plan - Protocol #}JZP150-201-02

- Population-level summary: The mean change from Baseline to Week 12 in CAPS-5 total score for each randomized treatment group and the difference in means between each randomized treatment group compared to placebo.

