7.3. Hypotheses Testing

To evaluate the efficacy of JZP150 at doses of 4 mg/day and 0.3 mg/day compared with placebo, pairwise comparisons between each of the doses and placebo will be conducted at the end of Week 12 for the primary and key secondary endpoints, resulting in up to six separate null hypotheses to be tested.

The null (H_{0i}) and alternative (H_{Ai}) hypotheses for analysis of the primary efficacy and key secondary efficacy variables (CAPS-5, CGI-S and PGI-S) at each of JZP150 4 mg and 0.3 mg vs placebo are:

$H_{01}(\text{CAPS-5})$: $\Delta\mu(\text{JZP150, 4 mg}) = \Delta\mu(\text{Placebo})$ vs $H_{A1}(\text{CAPS-5})$: $\Delta\mu(\text{JZP150, 4 mg}) \neq \Delta\mu(\text{Placebo})$

$H_{02}(\text{CGI-S})$: $\Delta\mu(\text{JZP150, 4 mg}) = \Delta\mu(\text{Placebo})$ vs. $H_{A2}(\text{CGI-S})$: $\Delta\mu(\text{JZP150, 4 mg}) \neq \Delta\mu(\text{Placebo})$

$H_{03}(\text{PGI-S})$: $\Delta\mu(\text{JZP150, 4 mg}) = \Delta\mu(\text{Placebo})$ vs $H_{A3}(\text{PGI-S})$: $\Delta\mu(\text{JZP150, 4 mg}) \neq \Delta\mu(\text{Placebo})$

Jazz Pharmaceuticals
 {Statistical Analysis Plan - Protocol #}JZP150-201-02

H₀₄(CAPS-5): $\Delta\mu_{(JZP150, 0.3 \text{ mg})} = \Delta\mu_{(\text{Placebo})}$ vs H_{A4}(CAPS-5): $\Delta\mu_{(JZP150, 0.3 \text{ mg})} \neq \Delta\mu_{(\text{Placebo})}$
 H₀₅(CGI-S): $\Delta\mu_{(JZP150, 0.3 \text{ mg})} = \Delta\mu_{(\text{Placebo})}$ vs H_{A5}(CGI-S): $\Delta\mu_{(JZP150, 0.3 \text{ mg})} \neq \Delta\mu_{(\text{Placebo})}$
 H₀₆(PGI-S): $\Delta\mu_{(JZP150, 0.3 \text{ mg})} = \Delta\mu_{(\text{Placebo})}$ vs H_{A6}(PGI-S): $\Delta\mu_{(JZP150, 0.3 \text{ mg})} \neq \Delta\mu_{(\text{Placebo})}$

where $\Delta\mu$ represents mean change from baseline to end of Week 12 in the CAPS-5 total score, CGI-S or PGI-S.

Specifically, for the primary endpoint, the null hypothesis states that there is no difference in the mean change in the CAPS-5 total score from Baseline to Week 12 between the indicated JZP150 dose level and placebo arm. The alternative hypothesis states that the mean change in the CAPS-5 total score is not equal between the indicated JZP150 dose level and placebo.

The null and alternative hypotheses for each of the key secondary estimand variables (CGI-S and PGI-S) are defined similarly as for the primary efficacy estimand variable.

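### The SAS code specified for the non-parametric sensitivity analysis does not produce the Week 12 dose-versus-placebo results its text promises

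*SAP*

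**What the plan says.** SAP 9.1.3.3 describes a sensitivity analysis that may be run if there is strong evidence of non-normality. It promises two results. One is a test: "the p-value for comparing treatments for the primary endpoint will be reported from a non-parametric MMRM model". The other is a Hodges-Lehmann estimate with asymptotic 95% CI: "The estimated median difference between the change in CAPS-5 total score between each treatment group and placebo".

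The target is set elsewhere. SAP 4.2.1 gives "Variable (endpoint): CAPS-5 total score change from Baseline to Week 12", and SAP 7.3 says the pairwise comparisons of each dose with placebo "will be conducted at the end of Week 12 for the primary and key secondary endpoints".

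Section 9.1.3.3 then states "The following SAS code will be used" and lists three steps: a ranking of baseline and change, a `PROC MIXED` on the ranks with week as the repeated factor, and "PROC NPAR1WAY HL ALPHA=.05 DATA=ANAL" with treatment as the class variable and change as the analysis variable.

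The text lists the model terms as treatment, week, "treatment group by week interaction, randomization stratum and ranked baseline CAPS-5 total score as fixed effects". The code reads "MODEL RCHG = RBASE TRT WEEK TRT*WEEK RBASE* WEEK STRATUM" and continues with the stratum-by-week term.

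**The concern.** The SAP presents this as the code to be used, whereas the code in 9.1.2 is labelled an example. Code with that status should deliver the stated result, and here neither promised result comes out.

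The practical risk lies in a partial repair. Hodges-Lehmann is a two-sample estimator, so a programmer will see that the three arms must be cut to two. Nothing in the code prompts the same person to drop the Week 4 rows. The step would then run cleanly and return a plausible number that mixes the two visits, with a CI that counts two rows per person as independent.

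**Working it through.** **1. What the dataset holds.** The ranking step reads `ANAL` and writes the file used by `PROC MIXED`, where week is the repeated factor. `ANAL` must therefore contain every post-baseline CAPS-5 visit. SAP 9.1.1 gives two, Weeks 4 and 12, and the design has three arms. The Hodges-Lehmann step reads the same `ANAL` with no `WHERE` or `BY` statement.

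**2. What the rank model prints.** It goes from the `REPEATED` statement straight to `RUN`. With 3 arms and 2 visits, the treatment tests are:
- treatment: 3 − 1 = 2 df, averaged over visits;
- treatment-by-week: (3 − 1) × (2 − 1) = 2 df.

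Neither is a Week 12 comparison of one dose with placebo, and two such p-values are needed.

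**3. Comparison with the SAP's other code.** The main model in 9.1.2 has an `LSMEANS TRT*WEEK` statement with differences and CIs. The tipping-point code in 9.1.3.1 filters to one arm pair and Week 12. The rank and Hodges-Lehmann block recurs in 9.2.6.3 for B-IPF, which is measured only at Baseline and Week 12, so no week filter is needed there. In 9.1.3.3 one is needed.

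**4. Text against code.** The text of 9.1.3.3 has no baseline-by-week or stratum-by-week term. The code has both and matches the main model in 9.1.2.

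**5. Row counts if the arms are subset and the week is not.** The inputs are the completer numbers in SAP 5.3 (75 placebo, 38 on 0.3 mg, 75 on 4 mg), each with both visits. These inputs, with a difference of 6 and SD 10.5, give power of 93.5% and 81.2% by the noncentral t, close to the stated 93.4% and 80.9%.
- 4 mg versus placebo: 2 × (75 + 75) = 300 rows instead of 150.
- 0.3 mg versus placebo: 2 × (38 + 75) = 226 rows instead of 113.

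**6. What the pooled estimate targets.** Let the effects (placebo minus active) be e4 and e12, and the placebo means p4 and p12. The pooled active-minus-placebo differences form four groups with means −e4, −e12, (p4 − p12 − e4) and (p12 − p4 − e12). With equal visit counts and a common SD, the first two are symmetric about −(e4 + e12)/2, and so are the last two. The median difference in size is therefore (e4 + e12)/2, whatever the placebo means or the between-visit correlation. With e12 = 6 from SAP 5.3 and e4 assumed:

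| Assumed Week 4 effect | Pooled value | Week 12 value |
|---|---|---|
| 0 | (0 + 6)/2 = 3.0 | 6 |
| 3 | (3 + 6)/2 = 4.5 | 6 |
| 6 | (6 + 6)/2 = 6.0 | 6 |

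Range check: 108 per arm at Week 4 (270 × 2/5) and 75 at Week 12 gives 2.4–2.5, 4.2 and 6.0. A Week 4 SD of 8.5 gives 2.8, 4.4 and 6.0.

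**7. What happens to the CI.** Doubling the rows alone scales the width by √(150/300) = 0.71. In simulation (75 versus 75, SD 10.5, 1,500 trials per setting, assumed correlation 0.3 and 0.7, two placebo patterns) the pooled-to-Week-12 width ratio was 0.70–0.75. Coverage of the averaged effect was 85.4–92.8%; the Week 12 CI covered its own target 94.3–95.7% of the time. A check with 38 versus 75 gave similar results: a ratio of about 0.70 and coverage of about 85–92%.

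**The case against.** The strongest reply is that the code is shorthand. The text already names the primary endpoint and each dose against placebo, and the sentence just above the Hodges-Lehmann step names the primary endpoint again. `ANAL` serves as a generic dataset name across the SAP: the responder code in 9.2.6.1 also leaves week and arm pair implicit. Someone who ranks the variables of the main model would naturally keep its LS-means statement. The distorted estimates in the working require a programmer to follow the text on arms and ignore it on the endpoint. They also rest on a Week 4 effect, Week 4 SD and correlation that the documents do not give. Finally, the analysis is conditional and sits outside the alpha-controlled sequence of SAP 7.4.

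Much of this stands. The intended quantity is not in doubt, a careful programmer could repair the code, and the size figures are illustrations. It does not remove the fault. Within 9.1.3.3 the dataset is the one feeding the repeated-measures model, the code is stated as the code to be used, and the code in 9.1.2 and 9.1.3.1 shows that the SAP writes the contrast or the Week 12 filter where it means one.

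**Conclusion.** The point holds, as a minor correction. Followed as written, the code in SAP 9.1.3.3 gives neither the two Week 12 p-values nor the two Week 12 Hodges-Lehmann estimates, and the text disagrees with the code on two model terms. This rests on reading the code and on Hodges-Lehmann being a two-sample method; no numerical assumption is needed. The primary analysis, its error rate and its power are unaffected.

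The numerical consequence is conditional. It arises only if the arms are subset and the week is not, and the estimate is off only if the Week 4 and Week 12 effects differ. The CI is too narrow even when they are equal.

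The same code could carry further. SAP 9.1.4 applies the overall parametric or non-parametric choice to each subgroup, although it does say the interaction is estimated for Week 12. SAP 9.2.3 calls for similar sensitivity analyses of CGI-S and PGI-S, which have four post-baseline visits. No figure is claimed for those.

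**What to change.** 1. Run the Hodges-Lehmann step twice, each time with `WHERE WEEK=12` and one dose plus placebo.
2. Add `LSMEANS TRT*WEEK / CL DIFF` to the rank model and report the two Week 12 dose-versus-placebo p-values.
3. Add the baseline-by-week and stratum-by-week terms to the text so that it agrees with the code and with SAP 9.1.2.
4. Apply the same Week 12 restriction wherever this analysis is used for CGI-S, PGI-S or subgroups.

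The ranking step has no `BY WEEK`, so the two visits are ranked together. The repair works either way, but the SAP could state which ranking is meant.

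The cost is a few lines of SAP code and one sentence of text. No new data are needed.
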